## Study Protocol

### Participants

A total of  $N = 58$  Mexican students in grades 1-5 across eight public elementary schools in Sinaloa, Mexico participated in the current study ( $M = 7.25$  students/school, range = 6-8). For each student, one parent and one teacher were designated as “primary” (meaning they would participate in CLS-FUERTE and implement the strategies) and asked to complete all measures. All data was collected at the students’ respective schools. See Table 2 for demographic information and Figure 1 for participant flow.

**Recruitment.** Recruitment occurred between May and September each year and began with invitations to school principals suggested by the local SEP. As described in the introduction, as part of our augmented outreach/recruitment plan for Mexico, we invited all families and personnel in participating schools to an informational gathering in September in which we showed a silent video depicting a child with attention and impulse-control difficulties (i.e., the Behavioral Impairment Video; Haack, Gerdes, Lawton, & Schneider, 2014). We encouraged families to contact us if interested in a program to help children similar to the child in the video. School personnel also identified candidate children and contacted families about participating. See Figure 1 for recruitment flow and number of students deemed ineligible at each step of recruitment.

**Screening.** Interested parents scheduled an appointment to screen for eligibility. If parents attended the screening appointment, reported willingness/ability to participate in sessions, and described at least six youth symptoms of inattention and/or hyperactivity with at least one area of related impairment (i.e., school, family, or social impairment), we scheduled meetings for baseline assessments.

**Baseline Assessment.** After completing informed consent procedures approved by UCSF Committee on Human Research, parents and teachers of successfully screened students completed questionnaires, including the Child Symptom Inventory (CSI-4; Gadow & Sprafkin, 1997), Impairment Rating Scale (IRS; Fabiano et al., 2006), and demographic/history form. Students meeting the following criteria were eligible to participate: (a) at least six CSI-4 inattention symptoms and/or six

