hyperactive/impulsive symptoms endorsed by parent or teacher as occurring often or very often, (b) at least one area of IRS functioning rated as  $\geq 3$  by both parent and teacher, thereby indicating cross-setting impairment, (c) a parent available to participate; and (d) a primary teacher agreeing to participate. The assessment and screening algorithm based on at least six symptoms per domain reported by parents or teachers has been used in previous school-based ADHD trials (Haack et al., 2018; Pfiffner et al., 2016) and is associated with strong predictive validity for ADHD (sensitivity = .80, specificity = .58; Gadow & Sprafkin, 2002) and ODD (sensitivity = .70, specificity = .90; Gadow & Sprafkin, 2002) diagnoses. Students taking medication were eligible as long as regimens were stable. Students with significant visual or hearing impairments, severe language delay, psychosis, or pervasive developmental disorder or who were in full-day special classrooms were excluded. Eligible students provided assent before participating.

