### **Study Design**

A 2-level (students, schools) cluster RCT design (Hayes & Moulton, 2009) accounted for treatment (CLS-FUERTE or BAU) within level 2 (schools). We randomized schools to CLS-FUERTE (school n = 4, student n = 28) or BAU (school n = 4, student n = 31). We determined our sample size based on practical considerations (i.e., previous CLS trial experience, years of funding). Each year, schools were divided into high or low Socioeconomic Status (SES) categories (determined by the Secretary of Public Education; SEP) after baseline assessments were completed in September. The first author coded schools to conceal their identity until treatment was assigned and a statistician randomized concealed ordered pairs to CLS-FUERTE or BAU using a random number generator. Those randomized to CLS-FUERTE received the intervention between October and December, followed by post assessments for all families in December each year.

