### **Data Analytic Approach**

We performed all statistical analyses using SPSS (Version 26; IBM Corp, 2019). We analyzed outcomes in three domains (i.e., ADHD and ODD symptoms, and overall impairment) separately for each rater (i.e., parent and teacher). Primary analyses involved generalized estimating equations (GEE) using the SPSS GENLIN procedure with unstructured correlation matrices to examine within (baseline; post-treatment) and between (CLS-FUERTE vs BAU) group comparisons, adjusting for school clustering. GEE was chosen over alternative methods due to relaxed distribution requirements. Analyses were completed initially without covariates. We then performed follow-up analyses adjusting for parental level of education and child age, gender, and ADHD medication status; however, inclusion did not change the pattern or interpretation of results. Therefore, simple analyses without covariates are presented. To control

for Type 1 Error, a Benjamini-Hochberg false discovery rate (FDR; Benjamini & Hochberg, 1995) was applied within domain. The FDR exerts a more powerful control over wrongly rejecting the null compared to other procedures that control for family-wise error (e.g., Bonferroni correction). For all pairwise comparisons, Hedges'  $g$  effect size metrics are provided. Hedges'  $g$  estimates are Cohen's  $d$  estimates corrected for the upward bias associated with smaller sample sizes. Interpretation of Hedges'  $g$  estimates are consistent with traditional effect size conventions (i.e., 0.2 = small; 0.5 = moderate; 0.8 = large).

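### The baseline score enters the presented GEE only as a time point, never as a covariate; unless baseline means were constrained equal, this usually costs precision

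*Combined protocol and SAP*

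**What the plan says.** Three domains (ADHD symptoms, ODD symptoms, overall impairment) are analysed separately for parent and teacher, so there are six outcomes. The Data Analytic Approach describes the primary model as a GEE with unstructured correlation matrices, used "to examine within (baseline; post-treatment) and between (CLS-FUERTE vs BAU) group comparisons, adjusting for school clustering". Baseline is therefore a level of the within factor, that is, part of the outcome vector.

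The first analyses had no covariates. The next step was: "We then performed follow-up analyses adjusting for parental level of education and child age, gender, and ADHD medication status". The baseline score is not on that list. The section ends: "Therefore, simple analyses without covariates are presented".

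The model terms are not written out. The section does not say whether the treatment effect is the arm-by-time contrast or the arm difference at post-treatment; effect sizes are promised "For all pairwise comparisons", which leaves the second reading open. It also does not say whether the arms share a common baseline mean.

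Study Design places SES classification "after baseline assessments were completed in September", with random assignment described next. The baseline score is thus a pre-randomisation variable.

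**The concern.** Baseline severity usually predicts post-treatment severity on the same scale. When a score was taken before allocation, regressing the post score on arm and baseline is normally the most precise simple estimate of the treatment effect. A difference in mean change fixes the baseline slope at 1, and a post-only difference fixes it at 0. Neither is generally the best value.

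An unstructured working correlation does not repair this. With two occasions, complete data and free arm-by-time means, the fitted means are essentially the observed cell means, whatever the correlation. Only a common baseline mean lets the correlation carry baseline information into the treatment effect.

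The stake is precision. The trial has eight schools, and Study Design says the sample size rested on practical grounds. Wider intervals than the data require matter here.

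**Working it through.** **No plan figure to reproduce.** The documents give no outcome SD, ICC, pre-post correlation or power calculation. All three quantities are assumed below, and ranges are shown.

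**Inputs.** From the documents: 8 schools, 58 students, mean 7.25 per school (8 × 7.25 = 58; the arm sizes in Study Design sum to 28 + 31 = 59, which does not affect the ratios). Assumed: pre-post correlation ρ = 0.3, 0.5, 0.7; k = baseline SD / post SD.

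**Step 1: equal correlation at both levels.** With post variance 1, the variance of each contrast is proportional to:

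- change: 1 + k² − 2ρk
- post-only: 1
- baseline-adjusted, or common baseline mean: 1 − ρ²

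The SE ratios to the adjusted analysis are √[(1 + k² − 2ρk)/(1 − ρ²)] and 1/√(1 − ρ²). Example, k = 1, ρ = 0.3: √(1.4/0.91) = 1.240. Example, k = 0.8, ρ = 0.7: √(0.52/0.51) = 1.010.

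| Contrast | ρ = 0.3 | ρ = 0.5 | ρ = 0.7 |
|---|---|---|---|
| Change, k = 1 | 1.240 | 1.155 | 1.085 |
| Change, k = 0.8 | 1.129 | 1.058 | 1.010 |
| Change, k = 1.25 | 1.411 | 1.323 | 1.262 |
| Post-only, any k | 1.048 | 1.155 | 1.400 |

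The change ratio can also be written √[1 + (k − ρ)²/(1 − ρ²)], so here the loss is zero only when k = ρ.

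**Step 2: which k?** Eligibility criterion (a) in Participants is a severity threshold: a minimum count of inattention symptoms or of "hyperactive/impulsive symptoms endorsed by parent or teacher as occurring often or very often". Selecting on severity can compress the baseline spread, which makes k below 1 plausible for some outcomes. It does not settle k for all six: ODD symptoms are not an entry criterion, and because either rater suffices, one rater's ADHD score need not be truncated.

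**Step 3: school-level correlation differs from student-level.** Let c be the ICC (assumed equal at both occasions), r the school-level correlation and m = 7.25, with the slope ρ/k estimated within schools. The variance of a school mean is:

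- change: c(1 + k² − 2kr) + (1 − c)(1 + k² − 2kρ)/m
- adjusted: c(1 + ρ² − 2ρr) + (1 − c)(1 − ρ²)/m

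At c = 0.15, r = 1, k = 1, ρ = 0.3:

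- change: 0 + 0.85 × 1.4/7.25 = 0.1641
- adjusted: 0.15 × 0.49 + 0.85 × 0.91/7.25 = 0.1802
- SE ratio: √(0.1641/0.1802) = 0.954

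For ρ = 0.3, 0.5, 0.7 the ratios are 0.954, 0.967, 0.980 (k = 1) and 0.888, 0.913, 0.956 (k = 0.8). In this corner the change contrast is the more precise. At c = 0.05, r = 1, k = 1 the ratios are 1.130, 1.088, 1.050, so the loss returns.

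**Step 4: simulation with clustering.** Settings: 8 schools, 58 students, equal SDs, student-level ρ 0.3 to 0.8, 4,000 runs per setting. SE ratios, change to adjusted:

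- ICC 0 to 0.05: 1.03 to 1.26
- ICC 0.15, school-level correlation 0.2 or equal to ρ: 1.04 to 1.24
- ICC 0.15, school-level correlation 0.95: 0.99 to 1.01

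Post-only to adjusted ran from 1.03 to 2.14 over all settings.

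**The case against.** **A change contrast already uses baseline.** This stands. Compared with post-only, its variance is smaller whenever k < 2ρ. At ρ = 0.7, k = 1 its SE is √0.6 = 0.775 of the post-only SE, about 23% lower; at ρ = 0.5, k = 0.8 it is √0.84 = 0.917, about 8% lower. A reader might infer that baseline was ignored. The documents support that only under the post-only reading; under the change reading baseline is used, but inefficiently.

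**The loss is conditional.** This also stands. A GEE with a common baseline mean, and a working correlation that carries the within-student pre-post correlation, would already recover the precision. The text is silent on this. Even with free means, the loss can be about 1% (k = 0.8, ρ = 0.7) or reverse (Step 3).

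**Covariates were tried and changed nothing.** This does not answer the point. That statement covers parental education, age, gender and medication, not the baseline score.

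**The analyses are finished.** True. An adjusted model added now is post hoc, so it supplements the presented analysis and does not replace it.

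**The SES category is in no listed model either.** Study Design says "Each year, schools were divided into high or low Socioeconomic Status (SES) categories", and it is tempting to fold this and small-sample inference into one remedy. They are separate questions. An SES term takes a school-level degree of freedom (t critical value 2.447 on 6 df, 2.571 on 5 df) and could cancel the gain sought here.

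**Conclusion.** The concern holds as a point about precision. The baseline score is in no listed covariate set, and no equal-baseline constraint is stated. That it was not a covariate is inferred from the listed terms, since the model is not written out.

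With free arm-by-time means, complete data, equal school- and student-level correlation and assumed ρ of 0.3, 0.5 and 0.7, the SE excess is 24, 15 and 8% for a change contrast with equal SDs. It is 13, 6 and 1% with the baseline SD at 0.8 of the post SD, and 5, 15 and 40% for a post-only contrast. The loss is usual, not universal, and the documents do not fix its size.

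A reader might infer a biased effect or a favourable choice of model. The documents support neither: schools were allocated after baseline, so the contrasts differ in efficiency, and nothing shows that the choice was driven by results.

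**What to change.** For each of the six domain-by-rater outcomes, add an analysis of the post-treatment score on arm plus the baseline score of the same measure from the same rater, with school as the cluster. A GEE with a common baseline mean is an equivalent form if its working correlation carries the pre-post correlation. Use the same inference method as the analysis it is compared with, so that any change in interval width comes from the baseline term alone.

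Estimate the baseline slope from student data. On eight school means, estimating the slope multiplies the variance by about 1 + 1/(8 − 4) = 1.25, so at k = 1 adjustment beats change only if 1.25(1 + ρ)/2 < 1, that is, ρ < 0.6. With 58 students the factor is 1 + 1/54 = 1.019.

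Report the result beside the existing GEE. For that GEE, state the contrast tested and whether baseline means were free or common. Label the adjusted model as specified after results were known. Keep the four existing covariates as sensitivity analyses, and take up SES adjustment and small-sample school-level inference separately.

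Cost: a modest re-analysis of data already held, post hoc status, and little or no gain in some scenarios.

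### Hedges' g is tied to undefined pairs with no stated interval, and its small/moderate/large labels are finer than eight schools can support

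*Combined protocol and SAP*

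**What the plan says.** All of the effect-size plan is in Data Analytic Approach. The primary GEE is used "to examine within (baseline; post-treatment) and between (CLS-FUERTE vs BAU) group comparisons, adjusting for school clustering". Effect sizes follow: "For all pairwise comparisons", Hedges' g is given. It is described as Cohen's d "estimates corrected for the upward bias associated with smaller sample sizes". On interpretation, the plan states that "estimates are consistent with traditional effect size conventions (i.e., 0.2 = small; 0.5 = moderate; 0.8 = large".

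The section does not say which pairs are meant, which SD is the divisor, or whether g will have an interval. The baseline score enters as one of the two repeated outcomes. It is not among the covariates of the follow-up analyses (parental education, child age, gender and medication status).

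Study Design gives the scale of the trial: "We randomized schools to CLS-FUERTE (school n = 4, student n = 28) or BAU (school n = 4, student n = 31". It states no target effect or precision: "We determined our sample size based on practical considerations (i.e., previous CLS trial experience, years of funding".

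**The concern.** Two arms and two occasions make four cell means. Pairwise comparisons of those cells are pre-post differences within an arm or arm differences at one occasion.

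- **Within-arm g.** This mixes any treatment effect with time trend over the school term and with regression to the mean. The latter is a real possibility because students entered on high symptom counts and impairment ratings (Participants, Baseline Assessment).
- **Between-arm g at post-treatment.** This is protected by randomization, but unadjusted it includes whatever baseline difference chance left between four schools and four others.

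Both kinds would be read against the same three labels. A reader will tend to take the label as the size of the treatment effect. That needs a contrast that estimates the treatment effect, and enough precision to tell neighbouring labels, 0.3 apart, from each other. The small-sample correction supplies neither.

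**Working it through.** The plan states no power, target effect or precision for g, so there is no figure of its own to reproduce. One check on the inputs: 58/8 = 7.25 agrees with the stated mean per school, but 28 + 31 = 59 does not agree with N = 58. Using 28/30 or 27/31 instead of 28/31 changes the half-widths in step 2 by at most 0.01.

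**Inputs.** From the documents: 28 and 31 students, 4 and 4 schools, labels at 0.2, 0.5 and 0.8. Assumed, because the documents give none: ICC 0 to 0.20; pre-post correlation r from 0.3 to 0.9, taken as equal at school and student level; two-sided 95% intervals; 8 − 2 = 6 degrees of freedom, with t = 2.447.

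**1. What the small-sample correction does.** J = 1 − 3/(4 × 57 − 1) = 1 − 3/227 = 0.987. It shrinks g by 1.3%. It corrects bias and says nothing about precision or clustering.

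**2. Precision of an unadjusted post-treatment between-arm g.** SE = √[(1/28 + 1/31)(1 + (m − 1)ICC)], with m = 59/8 = 7.375. The half-width is 2.447 × SE.

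| ICC | 1 + 6.375 × ICC | SE | Half-width | Interval around g = 0.5 |
|---|---|---|---|---|
| 0 | 1.00 | 0.261 | 0.64 | −0.14 to 1.14 |
| 0.05 | 1.32 | 0.299 | 0.73 | −0.23 to 1.23 |
| 0.10 | 1.64 | 0.334 | 0.82 | −0.32 to 1.32 |
| 0.20 | 2.28 | 0.393 | 0.96 | −0.46 to 1.46 |

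Every row contains both 0.2 and 0.8. Even with 59 independent students and a normal interval, the half-width would be about 0.51.

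**3. Effect of using baseline.** Relative to step 2, the SE is multiplied by √(1 − r²) for a baseline-adjusted post difference and by √(2(1 − r)) for a raw change score. Half-widths in raw-SD units, adjusted / change:

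| r | Factors | ICC 0 | ICC 0.10 | ICC 0.20 |
|---|---|---|---|---|
| 0.3 | 0.954 / 1.183 | 0.61 / 0.75 | 0.78 / 0.97 | 0.92 / 1.14 |
| 0.5 | 0.866 / 1.000 | 0.55 / 0.64 | 0.71 / 0.82 | 0.83 / 0.96 |
| 0.7 | 0.714 / 0.775 | 0.46 / 0.49 | 0.58 / 0.63 | 0.69 / 0.75 |
| 0.9 | 0.436 / 0.447 | 0.28 / 0.29 | 0.36 / 0.37 | 0.42 / 0.43 |

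Below r = 0.5 the change score is noisier than the unadjusted post difference. The adjusted difference is not noisier than either at any r shown. Only at r = 0.9 with ICC 0 does a half-width fall below the 0.3 gap between labels.

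**4. Chance baseline imbalance.** A baseline difference between arms has the same SE as in step 2. By a normal approximation, the chance that it exceeds 0.2 SD in either direction is 2[1 − Φ(0.2/SE)] = 44%, 55% and 61% at ICC 0, 0.10 and 0.20. On average a fraction r of that difference carries into the unadjusted post-treatment g. Grouping schools by SES could reduce this by an amount the documents do not allow one to compute.

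**5. The divisor.** A difference in change of 0.5 raw SD becomes 0.5/√(2(1 − r)) in change-SD units: 0.42 at r = 0.3, 0.65 at r = 0.7 and 1.12 at r = 0.9. The choice of SD alone can move the label.

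**The case against.** Several stronger readings are tempting, and the documents do not support them.

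- **That the reported g is not an effect size for the randomized comparison.** The pairs are never defined, so this cannot be stated as fact. Treatment was assigned after baseline, so a post-treatment between-arm difference is a randomized contrast with the same target as the difference in change. They differ in efficiency, and the change score gains only if r exceeds about 0.5.
- **That the p-value and the effect size describe different contrasts.** The section lists within- and between-group comparisons and then gives g for pairwise comparisons. These may be the same set. A mismatch arises only if a separate arm-by-time test is presumed, and none is named.
- **That a post-only and a change-based g would usually carry different labels.** How often they would depends on the true effect and the correlation. The documents give neither, and do not say whether the three values are cut points or benchmarks.
- **That clustering is ignored.** The GEE comparisons are adjusted for school. What is missing is narrower: an interval for g that reflects it.

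It is also fair to say that the labels are a descriptive convention. They drive no test, no false-discovery step and no decision, and the plan does not call within-arm g a treatment effect. With a very high pre-post correlation and little clustering, the precision problem largely goes away.

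These points limit the concern but do not remove it. Followed as written and read naturally, the rule puts within-arm values and unadjusted between-arm values under labels that the design cannot tell apart over most of the plausible range.

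**Conclusion.** The point holds as a weakness of reporting and interpretation, not as an error in the primary test. The contrast and the divisor behind g are unspecified, no interval is mentioned, and the natural reading includes within-arm values that are not treatment effects.

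For an unadjusted post-treatment between-arm g, the half-width is about 0.64 to 0.96, so a label of moderate at 0.5 cannot be distinguished from small or large. This rests on the assumed ICC of 0 to 0.20 and on 6 degrees of freedom. Baseline adjustment narrows it, to 0.46 to 0.69 at r = 0.7, which is still wider than the spacing of the labels. An analysis by school pairs would have only 3 degrees of freedom, and the ICC may differ between raw and baseline-adjusted scores, so the figures are a guide to scale. The change is worth making because a better estimate is available from data already collected.

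**What to change.** For each outcome and rater, report one treatment-effect g:

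- **Contrast:** the post-treatment difference between arms, adjusted for the baseline score. This is preferable to a raw change score, which is noisier when r is below about 0.5.
- **Divisor:** one SD pooled over both arms, with the occasion stated, and the same choice for all outcomes.
- **Interval:** 95%, from the school-level standard error with school-level degrees of freedom. State the number used; it falls from 6 to 5 if a school-level baseline covariate is fitted.
- **Wording:** describe the range of effects that the interval allows, and do not attach a label to the point value alone.
- **Within-arm g:** keep as description only, marked as not estimating the treatment effect.

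Reconcile 58 with 28 + 31 = 59 at the same time, so that the denominators are clear.

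This needs no new data: one baseline-adjusted model per outcome and rater, a short calculation and a revised effect-size column. The cost is in presentation, with wide intervals and fewer statements that an effect is moderate or large.
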